## 2. Specific Aims / Objectives

Electronic cigarettes (e-cigs) deliver nicotine, flavorings, and carriers through heated aerosols. The use of e-cigs generally, and as an occasional and regular use alternative to smoking, is growing at an extraordinary rate. The FDA has recently deemed the authority to regulate e-cigs, but regulatory decisions require safety data. It is plausible that the e-cig use will induce lung toxicity by promoting inflammation, but data for this is a critical research gap. Studies of healthy smokers undergoing bronchoscopy demonstrate an effect on promoting inflammation, which is an important component for the pathogenesis of chronic obstructive pulmonary disease and lung cancer. It is plausible that e-cigs affect similar mechanisms, albeit at a lower amount. E-cig human biomarker studies (cross-sectional studies and clinical trials) demonstrate clear decreases in cigarette smoke exposure toxicants with complete switching. However, these studies assess blood and urine biomarkers, where it is unknown if the biomarkers are surrogates for lung biomarkers and inflammation.

In this application, we can take advantage of a new opportunity using the newly released National Institute on Drug Abuse (NIDA) standardized research e-cig (SREC), because this is a product that will likely not change over time subject to marketing and manufacturing influences, and allows for comparisons across studies. It also is available with and without nicotine. While there are numerous experimental laboratory studies underway to infer human lung toxicity (e.g., chemical, cell culture and animal studies about e-cig aerosol constituents), regulatory decisions will best be made with human data for actual e-cig use. It is well-established that cigarette smoke increases pulmonary inflammation contributing to lung disease and cancer. The availability for the SREC with and without nicotine provides a unique opportunity to assess the contribution of nicotine, a highly bioactive molecule, to lung toxicity. Nicotine is both pro- and anti-inflammatory, but more data weighs in for an overall anti-inflammatory effect and so that will be studied herein and hypothesized to attenuate the pro-inflammatory effects of e-cig aerosols.

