### iii. Intervention type/process

This study is a 10-week clinical trial (8 weeks on the experimental condition after a scheduled quit date; n=128) for healthy smokers randomized to one of four groups. The duration for the intervention period has been extended from 4 to 8 weeks to harmonize with two other NIDA grantees who are studying the SREC, at the request of NIDA. An overview is shown in **Figure 1**. Each group is 32 subjects. All subjects will undergo a baseline bronchoscopy. Bronchial brushings and BALs will be collected during the bronchoscopies to assess total and differential cell counts, inflammatory cytokines, mRNA gene expression, miRNA expression, genome methylation, microbiomes, proteomics, CyTOF, pulmonary function tests and BAL metabolomics. Subjects also will be assessed for THC exposure, exhaled FeNO, exhaled CO, and urinary PG and glycerin.

At the baseline bronchoscopy visit, subjects will be randomized to either one of the four groups (control and interventions). The SREC intervention groups will be instructed on how to use their assigned product and after the visit begin to use the device daily and will be allowed to continue smoking, in order for them to learn how to use the device. They will be told that after two weeks of use to begin their assigned condition, essentially establishing a smoking quit date (e-cig-only) on day 15. To mediate withdrawal symptoms and increase retention, subjects assigned to SREC placebo group will be offered varenicline at no cost, and used according to FDA indications. Those participants will be given the medication at the day 8 visit, one week before the day 15 quit date. The NRT group will begin to use the NRT one week before the day 15 quit date. This design allows for a rolling admission and increased contemporary controls in the event a device is not available at the time of enrollment. The conditions subjects are randomized to may vary depending on product availability.

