**E-liquid Characteristics:**

Nicotine-containing and placebo versions are “tobacco” flavored

Shelf-life at 25C - > 1 year (unopened)

Nicotine concentration - 5% w/w (corresponds to 58 mg / mL)

Propylene Glycol % - ~ 38.75% (wt / wt)

Glycerin % - ~ 50% (wt / wt)

**Product use:** At the first bronchoscopy visit, SREC users will be trained to use the product and given instructions on how to use the device. They will not be requested to use the device at the visit, but to use it at home representing the way real world e-cig users learn to use the product (product use will be observed one week later). An instructional video showing how to use the device may be provided at first bronchoscopy visit, and other visits as needed ([https://www.youtube.com/watch?v=lKcblA\\_AbTg](https://www.youtube.com/watch?v=lKcblA_AbTg)). Similar videos will be created for the other products as needed. Subjects in the SREC arms will be instructed that after two weeks of use, as they

learn to use the product and work towards complete substitution, they will begin their assignment effective on day 15.

E-cig users will be encouraged to use the product every 1-2 hours, and as needed to address cravings. Subjects will be allowed to smoke their usual brand of cigarettes *ad libitum* for the first 2 weeks and encouraged to reduce their cigarettes per day to 5 or less, followed by quitting cigarette smoking and avoiding cannabis use. Subjects will be contacted by phone or email after 72 hours of study product use, and there will be contact with the subject on a weekly basis (phone or visit). This two-week run-in period allows the subject to become accustomed to the product and have a specific quit date.

Subjects randomized to the placebo SREC will be offered varenicline, an FDA-approved smoking cessation medication, at no cost to limit withdrawal symptoms and increase study retention. Those participants will be given the medication at the day 8 visit, one week before the day 15 quit date.

Subjects randomized to NRT complete substitution will be instructed how to use the assigned product(s). Subjects will be asked to use patches (21mg) in combination with gum (4 mg) and/or lozenge (4 mg) . If appropriate, subjects may use a single product after discussion with study staff and/or the study PI. If subjects experience side effects, dosages can be reduced and/or products changed. The NRT group will begin to use the NRT at the day 8 visit, one week before the day 15 quit date.

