All intervention subjects will receive counseling with motivational interviewing in order to achieve compliance.

SREC Dispensing (targeted, but may be revised as needed): Participants will be provided two devices, in case one fails, including charging materials. Based on email and telephone conversations with the SREC manufacturer (NJOY), NIDA, and [name], a Cardiologist and Investigator at McGill University who is currently conducting a randomized clinical trial (Canadian E3 Trial) using a SREC device, we will assume that participants will use one tank/pod every two days (i.e., 0.5 tank/pod per day). At the anticipated rate, there will be 70 days on product or approximately 35 pods required.

Pods will be weighed and logged prior to dispensing. At each visit, the participant will be provided with a sufficient quantity of product for anticipated use and an additional 1 week of product. This will allow the participant to have enough product if the appointment is postponed or the participant uses more than anticipated. At the next visit, the participant will return used and unused product. Returned materials will be weighed. Unused/unopened product will be re-dispensed along with the necessary amount of new product. These estimates will vary depending on individual use. Dispensing will be adjusted to match product use. Participants can contact study staff to request additional product as needed. Participants will be asked to return all unused product and the devices at the end of the study.

Day	Days between visits 7	Pods to be dispensed*
Day 1 (W0) – BR1	7	7
Day 8 (W1) – visit	7	7
Day 15 (W2) – visit	7	7
Day 22 (W3) – visit	7	7
Day 29 (W4) – visit	14	11
Day 43 (W6) – visit	14	11
Day 57 (W8) – visit	14	11
Day 71 (W10) – visit	NA	

\*One week of additional product (~3 or 4 pods) may be distributed at each visit to provide sufficient quantity for any unanticipated use or delay in visit scheduling.

Varenicline dosing and dispensing (targeted, but may be revised as needed): Subjects randomly assigned to the Complete Substitution with the placebo SREC device will be offered up to 12 weeks of varenicline, a nicotinic receptor partial agonist indicated for use as an aid to smoking cessation treatment at no cost. The 12 week

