duration extends the use up to one month after the intervention to be consistent with FDA-approved uses. [name] (or other MD associated with the study) will review all subjects' medical history and evaluate the subject for indications and safety of the varenicline at the BR1 visit prior to the procedure. Subjects may continue in the study if they are not eligible to use varenicline or refuses.

The medication (see below) will be obtained from the OSUWMC or James Cancer Center pharmacy in bulk. Medications will be stored at room temperature (as recommended by the manufacturer) and in locked cabinets.

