#### Bottles

0.5 mg - bottle of 56 NDC 00069-0468-56

1 mg - bottle of 56 NDC 00069-0469-56

Medication will be labeled with the subject's study ID, "For Research Purposes", Study telephone number, Medication Name and strength, Instructions for use, Dispensed date, Expiration date, and Quantity. The research staff dispensing the medication will include their initials on the label and document the dispensation (and return of unused medication) on the product accountability log. Upon completion of the study or if the subject stops taking the medication, any medication that is returned by the subject will be taken to the pharmacy for appropriate disposal.

A general accounting of all varenicline medication obtained from the pharmacy and dispensed to subjects will be maintained by study personnel.

At each visit, the participant will be provided with a sufficient quantity of product for anticipated use and an additional 1 week of medication or given a 4 week card. This will allow the participant to have enough medication if the appointment is postponed. At the next visit, the participant will return unused medication, which will be recorded and redispensed as appropriate. Subjects will be monitored for adverse reaction using the same process as all other arms.

Patients will begin varenicline dosing one week before the day 15 quit date.

Starting Week: 0.5 mg once daily on days 1–3 and 0.5 mg twice daily on days 4–7.

Continuing Weeks: 1 mg twice daily for up to a total of 12 weeks.

Day	Days between visits+7	Daily dose	Tablets to be dispensed
Day 8 (W1) – visit	7 + 7 = 14	0.5 mg once daily for 3 days, then 0.5 mg twice daily for 4 days	22 tablets of 0.5 mg
Day 15 (W2) – visit	7 + 7 = 14	1 mg twice daily	28 tablets of 1 mg
Day 22 (W3) – visit	7 + 7 = 14	1 mg twice daily	28 tablets of 1 mg
Day 29 (W4) – visit	14 + 7 = 21	1 mg twice daily	42 tablets of 1 mg
Day 43 (W6) - visit	14 + 7 = 21	1 mg twice daily	42 tablets of 1 mg
Day 57 (W8) – visit	14 + 7 = 21	1 mg twice daily	42 tablets of 1 mg
Day 71 (W10) – BR2			Up to three weeks (21 tablets) to meet the FDA recommended duration

NRT dosing and dispensing (targeted, but may be revised as needed): Similar to the other conditions, NRT will be dispensed at each visit. Beginning at Day 8 (W1), the participant will be provided with a sufficient quantity of product for anticipated use and an additional 1 week of product. This will allow the participant to have enough

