**Table 1. Data Collection**

Measures	ORNT	Day 1/ BR1	Day 8/ Wk1	Calls 1-4: Day 4 Day 36 Day 50 Day 64	Day 15/ Wk2 Day 22/ Wk 3 Day 29/ Wk4 Day 43/ Wk 6 Day 57/ Wk8	Day 71/ BR2	3 Months Post BR2 Call
Contact & Physician Information	X						
Demographics	X						
Progress Note	X	X	X	X	X	X	X
Medical History (Baseline and Updates)	X	X	X	X	X	X	
Covid-19 Screener	X						
Covid-19 Follow Up	X	X	X	X	X		
Adverse Events	X	X	X	X	X	X	X
Concomitant Medications	X	X	X	X	X	X	X
Prime MD	X						
CESD	X				Day 29	X	X
SMAST	X						
Perceived Stress		X			Day 29	X	
Perceived Health Risk		X			Day 15	X	
Tobacco Use History*	X						
Social/Lifestyle History	X					X	
Environmental Exposure	X	X			Day 29	X	
Health Changes (Overall Health)**	X	X	X	X	X	X	
Alcohol and Drug Abuse History	X						
Alcohol Use***	X						
Supplements Use	X						
Occupational Exposure	X	X			Day 29	X	
Eligibility Checklist	X						
Smoking Dependence Motives (WISDM)	X		X		X	X	
Stages Of Change	X					X	X
FTND	X	X	X		X	X	X
FTND (Modified for SREC Users)					X (e-Cig)	X (e-Cig)	X (e-Cig)
MN Withdrawal Scale		X	X		X	X	
Smoking Urges		X	X		X	X	
Product Evaluation Scale (NRT)					X	X	X
Evaluation of Electronic Vaping Devices			X	X	X	X	X
Expectancies			X (e-Cig)		X (e-Cig)	X (e-Cig)	X (e-Cig)
Drug Effects/Liking			X (e-Cig)		X (e-Cig)	X (e-Cig)	X (e-Cig)

Interest In Switching or Quitting	X					X	
Vitals (Including Height and Weight)	X	X	X		X	X	
CO (Daily)	X	X	X	X	X	X	
FeNO Results		X				X	
24-Hour Urine Sample Collection Form		X				X	
Inhalation Assessment						X (e-Cig)	
Pulmonary Function Test		X				X	
Sample Collection Form		X				X	
Pre Bronchoscopy Questionnaire		X				X	
Lung Randomization		X				X	
BAL Collection Information		X				X	
Product Accountability Log		X (e-Cig)	X		X	X	
E-cig Cartridge/ Pod Weight Log		X (e-Cig)	X (e-Cig)		X (e-Cig)	X (e-Cig)	
Daily Use Summary (TLFB)	X	X	X	X	X	X	X
Daily Diary		X	X	X	X	X	
Product Compliance****		X (e-Cig)	X	X	X	X	
Cessation Counseling*****			X	X	X	X	X
Follow-Up Call							X
Change In Status	As Needed						
Protocol Deviation Report	As Needed						

\* Subjects will be asked to report their daily tobacco and/or product use by phone or internet

\*\*Similar to Respiratory and Global Health Questionnaire

\*\*\*Follow-up alcohol use is captured on the Daily Use Summary (TLFB)

\*\*\*\*Product Compliance will be administered to SREC subjects starting at BR1; NRT subjects will be asked to complete the questionnaire starting at Day 8/Wk 1

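### Nicotine SREC versus placebo SREC compares nicotine with placebo plus optional varenicline, so it does not isolate the effect of nicotine, and the SAP does not say so

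*Protocol*

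**What the plan says.** Protocol 4.a.iii (Intervention type/process) says that "subjects assigned to SREC placebo group will be offered varenicline at no cost", to ease withdrawal and improve retention. The product-use text in 4.c.i repeats the offer: "Subjects randomized to the placebo SREC will be offered varenicline, an FDA-approved smoking cessation medication, at no cost to limit withdrawal symptoms". The paragraph on varenicline dosing describes the drug as "a nicotinic receptor partial agonist indicated for use as an aid to smoking cessation treatment" and allows up to 12 weeks of it. The offer is optional: "Subjects may continue in the study if they are not eligible to use varenicline or refuses".

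Dosing begins at the day 8 visit and moves to 1 mg twice daily after the first week. The dispensing table lists 42 tablets at day 57 and, at BR2, "Up to three weeks (21 tablets) to meet the FDA recommended duration". Staff are to "document the dispensation (and return of unused medication) on the product accountability log", and Table 1 lists "Concomitant Medications" among the forms collected.

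On nicotine, protocol section 2 says that having the SREC with and without nicotine "provides a unique opportunity to assess the contribution of nicotine, a highly bioactive molecule, to lung toxicity". Its hypothesis predicts a smaller benefit for the nicotine-free device and gives nicotine's anti-inflammatory action as the reason. Section 3 presents the with-and-without comparison as the first step in showing a nicotine effect. Section 1, and the Summary of Significance and Innovation lists in section 3, also promise data on what nicotine does to the lung.

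The SAP describes the arm only as complete switching to the placebo SREC. Varenicline appears nowhere in the SAP or in protocol 4.g.

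**The concern.** The two SREC arms differ in two ways: nicotine in the e-liquid, and an offer of a drug that acts on nicotinic receptors. Section 3 of the protocol suggests that nicotine's anti-inflammatory effect may run through those receptors in lung and other cells. It cites nicotinic agonists as reducing acute lung injury and macrophage nicotinic receptors as lowering pro-inflammatory cytokines. Macrophage phenotype and cytokines are among the primary outcomes. On the protocol's own reasoning, then, the no-nicotine comparator may be receiving a drug that acts on the pathway under test.

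At stake is how the SREC-arm contrast is read. If varenicline does part of what nicotine does, the arms look alike, and a null could be reported as nicotine having no effect on the lung. The protocol says that the data are meant to inform FDA regulation, including of nicotine content, so that misreading would matter.

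**Working it through.** **1. Are users scheduled to be on varenicline at BR2?** Inputs are from the dosing text and dispensing table in protocol 4.c.i: start at day 8, BR2 at day 71 (window 3 days either side), up to 12 weeks, and 42 tablets at day 57 taken twice daily.
- Exposure before BR2: 71 − 8 = 63 days (9 weeks) of a possible 12 × 7 = 84, so a full course ends at about day 8 + 84 = 92.
- Day 57 supply: 42 / 2 = 21 days, to day 78. Seven of those days are the scheduling buffer; without it the supply runs to day 57 + 14 = 71, the BR2 date.
- Tablets handed out at BR2 cannot affect BR2 samples. They show only that the course is meant to be still running.

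So a subject who accepts and continues is on drug when the outcome is sampled.

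**2. Where does the SAP make this contrast?** SAP item 2 names comparisons with controls, and item 3 gives power for each condition against controls. Those comparisons do not test nicotine. The SREC-arm contrast enters through the pairwise form of Model 1 in item 3 (follow-up on baseline and arm) and through the secondary mtDNA analysis in item 7, which counts 4 × 3 / 2 = 6 arm pairs. Neither has a varenicline term or caveat. The covariates named as examples in item 2 are baseline smoking, FTND and gender.

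**3. The plan's power figure.** SAP item 3 and protocol 4.g give 80% power for a 1.5-fold difference in cell counts at 21 per group, two-sided 0.0001, CV 0.26. On the log scale, SD = √ln(1 + 0.26²) = 0.256. A noncentral-t calculation then needs 22 per group, and at 21 gives 77.7% power, with 80% reached at 1.51-fold. The figure reproduces to rounding. It is for a condition against control and is used below only as a reference size.

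**4. Illustration of attenuation.** None of these inputs is in the documents: u, the share of the placebo-SREC arm on varenicline; f, varenicline's effect on the biomarker as a share of nicotine's; T, the true nicotine fold effect. Assume u from 0.25 to 1, f from 0 to 1, and T = 1.5. On the log scale the nicotine arm is shifted by ln T and the placebo arm by u·f·ln T, so the contrast shows (1 − u·f)·ln T, an apparent fold of T^(1 − u·f). For example, u = 0.5 and f = 0.5 give 1.5^0.75 = 1.36.

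| u | f = 0 | f = 0.5 | f = 1 | Power at f = 1, 21 v 21, 0.0001 |
|---|---|---|---|---|
| 0.25 | 1.50 | 1.43 | 1.36 | 35% |
| 0.50 | 1.50 | 1.36 | 1.22 | 6% |
| 0.75 | 1.50 | 1.29 | 1.11 | 0.3% |
| 1.00 | 1.50 | 1.22 | 1.00 | 0.01% |

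At f = 0 power stays at 78%. The bottom right cell needs every subject to take varenicline and a partial agonist to match nicotine fully, so it is a bound, not an expectation. The 0.0001 threshold is the planning value; the SAP will use FDR in practice.

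**5. Would an analysis by varenicline use recover the nicotine effect?** No. Use occurs in one arm only, and takers choose themselves. Of about 21 placebo-SREC completers, non-takers would number about 16, 10 or 5 at u = 0.25, 0.50 or 0.75. The detectable fold against 21 nicotine-SREC completers would rise to 1.57, 1.71 or 2.04, in a comparison that is no longer randomised.

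**The case against.** The strongest reply has three parts.

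First, the design is open and reasoned. The protocol gives retention and withdrawal as the reasons for the offer, and its Randomization paragraph itself refers to subjects assigned placebo together with varenicline. This stands, and it is why varenicline should stay. SAP item 1 analyses completers, so withdrawing the drug could raise dropout or relapse in the placebo arm and distort the same contrast.

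Second, no named or powered comparison is a test of nicotine. This also stands and limits the point. Nicotine SREC versus control or NRT is untouched. Placebo SREC versus control, read as a nicotine-free e-cigarette effect, is affected only so far as varenicline acts directly on the biomarkers; where it only helps subjects stop smoking, it delivers the assigned condition. But the section 2 hypothesis cannot be assessed without the SREC-arm contrast, and the SAP's pairwise models will produce it.

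Third, nothing in the documents shows that varenicline affects the lung. That is right: the link is inferred from the drug class and the receptor argument, and the figures above show a possibility, not an estimate.

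A reader might go further and infer that varenicline could manufacture or inflate a nicotine effect by some stated amount. The documents do not support that. Section 3 does cite data that nicotinic receptors raise inflammation in human lung, but if so, nicotine and a partial agonist would both push upward and the contrast would still shrink. Inflation needs opposite net effects, for example nicotine acting mainly by another route. Because section 3 gives nicotine both pro- and anti-inflammatory actions, that cannot be excluded, but no size can be put on it.

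**Conclusion.** The point holds as one about what the contrast estimates and how it may be reported. The facts are certain from the text: one arm only, a schedule that covers BR2, optional uptake, a claim about nicotine in several protocol sections, and no mention in the SAP or protocol 4.g. Nicotine SREC versus placebo SREC is a comparison with placebo SREC with varenicline offered.

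The direction is less certain. Attenuation toward no difference is likeliest on the protocol's receptor argument, so a null is the main risk of misreading. The size cannot be computed: uptake and varenicline's lung effect are unknown, and there is no direct bias if that effect is nil. A reader might also infer that the nicotine comparison is worthless or that the comparisons with control fail. Neither follows: the first depends on those two unknowns, and most of the second does not involve this arm. It should be fixed before results are reported, because the correction is cheap and changes what may be concluded.

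**What to change.** Keep varenicline, and leave the models and sample size as they are.

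1. Add to the SAP: *Every contrast with the placebo-SREC arm is a contrast with placebo SREC with varenicline offered. Neither a difference nor a null result between the SREC arms will be attributed to nicotine alone unless the varenicline-use table shows negligible use.* State in the same paragraph what counts as negligible, before outcomes by arm are examined.
2. At the next amendment, align the nicotine-effect wording in protocol section 1, section 2 (rationale and hypothesis) and section 3 (the nicotine discussion, Summary of Significance and Innovation).
3. From the accountability log and the concomitant-medication form, tabulate how many placebo-SREC subjects started varenicline, for how long, and how many were on it at BR2. Do not compare outcomes by varenicline use.

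The cost is one SAP paragraph, one descriptive table from data already collected, and protocol wording edits that need an IRB amendment. The downside is a narrower claim about nicotine.
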